9.2 Sample Size Determination

Based on our preliminary studies in literature (83-87), we assume an anatomic success rate in LAVR group is about 70% at 24 months. The investigators believe that a difference in success rates less than 25% will not change clinical practice, but also that the sample size should be large enough so that an observed difference in success rates of 20% would be significant; i.e., an inability to differentiate between the procedures will require an observed difference that is less than 20%.

The study will be individually randomized group-treatment trial (IRGT), which patients are randomized to surgical interventions through a common surgeon (88-90). There will be three surgeons performing each surgical treatment. The number of surgeons and patients will be the same in each clinical site. We anticipate an average of 16 individually randomized patients per surgeon in each treatment group. Outcomes for patients treated by the same surgeon tend to be more similar. We assume minimal variability, estimating a small intraclass correlation coefficient (ICC) of 0.01. The table below illustrates power to detect at least 23% difference between treatment groups with varying assumptions on ICC and dropout rates. A total of 96 patients (48 patients per group) would yield 86% power to differentiate between anatomical success rates of 70% and 93% assuming an ICC of 0.01 and a two-sided 5% level of significance. Projecting a 20% dropout/loss to follow up rate over 2 years, we anticipate recruiting and up to 120 total patients.

ICC	% Dropout	Total patients	Average patients per surgeon	Power
0.01	0	120	20	92%
	10	108	18	90%
	20	96	16	86%
0.02	0	120	20	90%
	10	108	18	87%
	20	96	16	83%
0.05	0	120	20	82%
	10	108	18	79%
	20	96	16	76%

Due to concerns that ICC is higher than expected or dropout rate is higher than 20% toward the end of 2-year follow-up, we calculated the sample size that would be needed for 87% power to differentiate between anatomical success rates of 70% and 95% (a difference of 25%) in treatment groups with a two-sided 5% level of significance. The required sample size is 39 per group, or 78 total patients.

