9.4.2 Analysis of the Primary Efficacy Endpoint(s)

Anatomical Surgical Outcome

The primary endpoint for the surgical treatment is dichotomous: success or failure at 24 months after surgery. The primary outcome measure uses the rectal compression ratio at 24 months unless there has been retreatment at an earlier time. When there is retreatment, or when the 24-month ultrasound results and POPQ results are missing and the last observed measurements were consistent with the definition of failure, then the results at 24 months will be imputed to be a failure. A sensitivity analysis will be performed to study the effect on the primary endpoint of different methods of handling dropouts and missing data. It will be conducted by assuming various values for the imputed outcomes and comparing the results under those assumptions to the results of the primary analysis.

Cochran-Mantel-Haenszel (CMH) test will be used to compare between surgical treatments adjusting for stratification factor. In addition, Generalized linear mixed-effects models (GLMMs) will be performed to yield an effect estimate of conditional on surgeon. Demographics and other characteristics at baseline (treatment group, age, BMI, menopausal status, parity, duration and severity of ODS) will be included. Surgeon will be included as a random effect to account for

correlation between outcomes of patients treated by the same surgeon. Adjusted odds ratios (ORs) will be presented with 95% confidence intervals (CIs).

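### Section 9.2: the stated 86% power at ICC 0.01 is not reproduced by any valid two-sided 5% calculation tried that allows for surgeon clustering, and the 39-per-group fallback states no ICC

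*Combined protocol and SAP*

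**What the plan says.** Section 9.2 describes an individually randomized group-treatment trial. "There will be three surgeons performing each surgical treatment", and "We anticipate an average of 16 individually randomized patients per surgeon in each treatment group". On clustering: "We assume minimal variability, estimating a small intraclass correlation coefficient (ICC) of 0.01". The headline is that "A total of 96 patients (48 patients per group) would yield 86% power to differentiate between anatomical success rates of 70% and 93" (percent), at that ICC and a two-sided 5% level.

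A nine-cell table follows: "The table below illustrates power to detect at least 23% difference between treatment groups with varying assumptions on ICC and dropout rates". Its entries for 120/108/96 patients (20/18/16 per surgeon) are:
- ICC 0.01: 92/90/86%
- ICC 0.02: 90/87/83%
- ICC 0.05: 82/79/76%

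The section then adds a fallback, introduced by "Due to concerns that ICC is higher than expected or dropout rate is higher than 20% toward the end of 2-year follow-up". It gives 87% power for 70% against 95%: "The required sample size is 39 per group, or 78 total patients". No ICC is stated for this figure.

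Section 9.4.2 compares the arms with a Cochran-Mantel-Haenszel (CMH) test adjusted for the stratification factor. It also plans a generalized linear mixed model reporting odds ratios, where "Surgeon will be included as a random effect to account for" correlation within surgeon.

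**The concern.** With only three surgeons per treatment, similarity of outcomes within surgeon is a main design risk, and this table is the plan's only display of how well the trial tolerates it. The 86% is presented as already allowing for an ICC of 0.01. If the allowance is missing or too small, a reader or the monitoring board would take the design to be more robust to clustering than its inputs support. The same applies to the 39 per group, which reads as protection against a higher ICC.

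**Working it through.** **Inputs (Section 9.2).** Success 70% vs 93%; 48 per group; 3 surgeons per treatment; m = 16 patients per surgeon (18 and 20 in the other columns); ICC 0.01, 0.02, 0.05; two-sided 5%. Allocation is 1:1 (Section 6.3). The plan names no power formula and no ICC scale, so those below are assumptions.

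**Formulas.** Effective n per group = n / [1 + (m − 1) × ICC]. Unpooled power = Φ(d / √[p1q1/n1 + p2q2/n2] − 1.96). Arcsine power = Φ(h / √[1/n1 + 1/n2] − 1.96), with h the arcsine difference.

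**1. No clustering.** With n = 48: √(0.2751/48) = 0.0757; 0.23/0.0757 = 3.04; power 86.0%. For 120/108/96 patients the unpooled values are 92.5/89.7/86.0%, against the printed ICC 0.01 row of 92/90/86.

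**2. Base case, ICC on the proportion scale.** Design effect 1 + 15 × 0.01 = 1.15; effective n = 48/1.15 = 41.7. √(0.2751/41.7) = 0.0812; 0.23/0.0812 = 2.83; power 80.9%. Arcsine gives 81.3%, pooled 78.3%.

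**3. Base case, ICC on the logit scale.** Surgeon variance = (0.01/0.99) × π²/3, with the intercept set to keep the marginal rates. This implies proportion-scale ICCs of 0.0069 (at 70%) and 0.0022 (at 93%), so effective n = 43.5 and 46.5. Power is 83.0% unpooled and 84.1% arcsine (about 81% pooled).

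**4. Whole table (power, %).**

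| ICC | Patients | Printed | Proportion, unpooled | Logit, unpooled | Logit, arcsine |
|---|---|---|---|---|---|
| 0.01 | 120 | 92 | 87.6 | 89.7 | 90.6 |
| 0.01 | 108 | 90 | 84.6 | 86.8 | 87.8 |
| 0.01 | 96 | 86 | 80.9 | 83.0 | 84.1 |
| 0.02 | 120 | 90 | 82.4 | 86.8 | 88.4 |
| 0.02 | 108 | 87 | 79.5 | 83.8 | 85.5 |
| 0.02 | 96 | 83 | 75.9 | 80.1 | 81.8 |
| 0.05 | 120 | 82 | 68.2 | 77.9 | 81.3 |
| 0.05 | 108 | 79 | 65.9 | 75.1 | 78.5 |
| 0.05 | 96 | 76 | 63.2 | 71.8 | 75.0 |

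Printed minus recomputed is 4 to 14 points, 2.3 to 4.2 points and 0.5 to 2.2 points in the last three columns respectively.

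**5. A test that ignores surgeon.** A simulated two-sided chi-square with beta-binomial clustering and three surgeons per arm gives about 85% at the headline. At ICC 0.05 it gives about 85/83/81%, above the printed 82/79/76. With both arms at 70% it rejects about 7% of the time at ICC 0.01 and 14–17% at ICC 0.05, so it is not a 5% test.

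**6. Fallback, independent patients.** 70% vs 95%, n = 39: √(0.2575/39) = 0.0813; 0.25/0.0813 = 3.08; power 86.8%. The stated 87% reproduces.

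**7. Fallback as 39 actual patients per group** (13 per surgeon). Design effects are 1.12/1.24/1.60 at ICC 0.01/0.02/0.05. Unpooled power is 82.8/78.9/68.2% on the proportion scale and 84.4/82.1/75.3% on the logit scale.

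**8. Fallback as 39 effective patients per group.** On the proportion scale, solving n / [1 + (n/3 − 1) × ICC] = 39 gives 44.4, 51.6 and 105.9 actual patients per group at the three ICCs. The planned numbers give:
- 96 patients at ICC 0.02: 48/1.30 = 36.9 effective, power 84.9% for 70% vs 95%.
- 120 patients at ICC 0.05: 60/1.95 = 30.8 effective, power 78.0%.

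On the logit scale these two cases give 88.2% and 86.3%, roughly the stated 87%.

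**The case against.** The strongest reply is that the CMH test, which Section 9.4.2 names first, does not include surgeon, and that an unadjusted chi-square at the stated inputs has about 85% power, close to 86%. That stands as a description of rejection rates, and it means the table is not too high for every conceivable test. It does not rescue the 86% as power at a two-sided 5% level, because clustering inflates that test's type I error.

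Second, on a logit-scale ICC with the arcsine formula the table is nearly reproduced, and the smallest gap (79 vs 78.5) is borderline rounding. The planned mixed model with odds ratios makes that scale plausible. This stands: the size of the discrepancy cannot be settled until the method is named, and the group-treatment references cited in Section 9.2 were not available for this check.

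Third, the surgeon count itself is unclear. Section 9.2 says the number of surgeons is equal at each site, but three per treatment cannot be split equally over two sites. If three per treatment at each site were meant, the arcsine values come within 0.8 to 2.3 points of the table, still below it. That reading conflicts with the printed 16/18/20 patients per surgeon.

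Fourth, Section 9.2 never claims that the 39 includes a clustering allowance, and the figure can be read as an effective number. On that reading the planned 96–120 patients fall short in some scenarios on the proportion scale, while the same two scenarios roughly meet 87% on the logit scale. What stands is the need to say which is meant.

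**Conclusion.** The 86% is not reproduced at the stated inputs by any valid two-sided 5% calculation tried that allows for surgeon clustering. The supportable headline is about 81% on a proportion-scale ICC (78.3% pooled) or about 83–84% on a logit-scale ICC (unpooled, arcsine). Both rest on three surgeons per treatment with 16 patients each and on the formulas above. The fallback's 87% holds for independent patients only.

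Three stronger inferences are not supported:
- A reader might infer that the ICC was left out of the calculation. The ICC 0.01 row coincides with the unclustered values, but the other two rows fall as the ICC rises, and the documents do not record the cause.
- A reader might infer a proven large error in every cell. The gap depends on an ICC scale that the plan does not state, and it is small on the most favourable one.
- A reader might infer that the trial needs more patients. At the planned ICC the unpooled and arcsine values stay at or above 80.9%, so the finding concerns what the plan reports, not the enrolment target.

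**What to change.** 1. Reconcile the number of surgeons and the patients per surgeon with the statement that surgeon numbers are equal at the two sites.
2. Restate the 86% and the nine-cell table for a surgeon-adjusted 5% test with design effect 1 + (m − 1) × ICC, naming the formula or software and the ICC scale. With the cluster sizes as printed, the base case becomes about 81% (proportion scale) or about 83–84% (logit scale). If a method from the cited references yields the printed values, name it and give its inputs.
3. Label the 39 per group as an effective sample size with no clustering allowance, or recompute it at the ICC it is meant to cover.

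The cost is protocol and SAP wording. Enrolment and data collection do not change; the stated power becomes slightly less favourable.

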9.3 Populations for Analyses

Modified Intent-to-treat (mITT) Population

The mITT population will include all randomized participants who received at least one post-op visit. Participants will be analyzed according to their randomized treatment assignment, regardless of the treatment actually received.

Safety Population

The safety population will include all participants who received any study treatment. All safety analyses will use the safety population. Participants will be analyzed according to the treatment they actually received, regardless of the treatment assigned.

Per-protocol (PP) Population

The PP population is a subset of the ITT population who completed the study without any major protocol violations. Analyses will exclude the following randomized participants: (83) those who did not receive TSR/LAVR surgery as planned; (84) those who died within 12 months of surgery and were not assessed on the primary outcome before their death; (85) those who withdrew from study and withdrew consent for use of their data.

Full Analysis Set (FAS)

The FAS will include all randomized participants who receive any study treatment and have at least one assessment since the baseline visit. Participants will be analyzed in their randomized treatment assignment, regardless of the treatment actually received.

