Participants will receive the allocated transvaginal sacrospinous rectopexy surgery along with or without CVPS or laparoscopic abdominal ventral rectopexy surgery with or without CVPS as indicated for each individual and as determined before surgery (exceptions are allowed during the surgery if the surgeon decides that changing the surgical plan is in the best interest of the patient; this will be recorded as a protocol deviation). CVPS includes vaginal prolapse repair surgeries (anterior vaginal repair, posterior repair, and vault suspension) and abdominal prolapse repair surgery (sacrocolpopexy). If the participants report stress urinary incontinence at baseline, they will also receive a Tension-Free Vaginal Tape (Advantage FitTM, Boston Scientific). The primary objective of the surgical intervention is to compare the surgical success of rectal hypermobility surgery using TSR to surgery using LAVR 24 months postoperatively. The secondary objectives include comparing the change in pelvic floor disorder symptoms including OD and fecal incontinence symptoms, QOL and the incidence of perioperative and postoperative complications of these two rectal suspension procedures. We will also describe the motivations and barriers for individual women's participation in women's health research at 24 months after surgery in all participants. Data collection will occur at baseline, surgery and during hospitalization, and at 2 weeks, and 2-, 12-, and 24-months postoperatively.

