6.2 Preparation/ Handling/ Storage/ Accountability

6.2.1 Acquisition and Accountability

At both study sites, all investigators will perform the dynamic pelvic ultrasound. MR defecography will be performed by trained personnel at each site. Transvaginal sacrospinous rectopexy will be performed by urogynecologists. Laparoscopic abdominal ventral rectopexy will be performed by colorectal surgeons.

Per Objective Structured Assessment of Technical Skill (OSATS), competency criteria for the novel transvaginal sacrospinous rectopexy will be performing three to five cases under the supervision of [name] [name] and/or [name] until achieving the following milestone:

1. The surgeon was able to perform all aspects of the procedure safely and competently.

A second or third year urogynecology fellow or a second-year colorectal fellow will be able to assist in the surgeries under the direct supervision of investigators.

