6.4 Study Intervention Compliance

Surgeons will comply with randomization assignments to the extent possible. Variations will be documented as protocol deviation and justification for allowing clinical decision-making to overrule randomized treatment assignment will be documented. Protocol deviations will be reviewed by both the IRB and the Data Safety Monitoring Board (DSMB).

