8.2 Safety and Other Assessments

Perioperative measures of morbidity include operative time (a risk factor for operative morbidity), estimated blood loss, and intra-operative and post-operative complications. Complications will be categorized using a modification of the Dindo Classification (77). Perioperative morbidity will be recorded at the completion of the surgery, at hospital discharge, and at the 2-week postoperative visit.

In addition, the following specific adverse events will be assessed and reported:

1. Intra-operative ureteral injury/obstruction (identified as no spill of urine from one or both ureteral orifices after prolonged observation (> 10 minutes) via cystoscopy; when indicated, other procedures may be used diagnostically or therapeutically, such as ureteral stent placement.)
2. Removal/replacement of vault suspension sutures to relieve intra-operative ureteral obstruction
3. Postoperative ureteral injury (delayed recognition)
4. Intra-operative neural injury (as determined by post-operative neuropathic pain or other neurologic sequelae) that was new onset: Neuropathic pain attributable to the vaginal vault suspension will be defined as "Acute-onset pain involving the buttock, groin and/or lower extremity, usually unilateral, occurring on the side or sides where vault suspension stitches have been placed and within one week of the index surgery requiring an alteration of routine postoperative care (e.g., nerve block, physical therapy, return to OR for suture removal, the addition of medications used to treat neuropathic pain such as anticonvulsants or tricyclic anti-depressants, or the increase or persistence of narcotic pain medication use beyond 14 days after surgery)."
5. Transfusion of blood products (e.g., whole blood, packed red blood cells, platelets)
6. Vaginal granulation tissue requiring treatment
7. Vaginal or perineal stricture (i.e., narrowing or scarring) prompting a treating physician to suggest or the participant to request treatment (surgical or non-surgical)
8. Rectal injury
9. Postoperative pain

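### Safety is grouped only by treatment received, with no rule for a converted or abandoned rectopexy and no table by randomised arm

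*Combined protocol and SAP*

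**What the plan says.** Section 9.3 defines who enters the safety set: "The safety population will include all participants who received any study treatment". It then makes that set the only one for safety ("All safety analyses will use the safety population") and fixes the grouping: "Participants will be analyzed according to the treatment they actually received, regardless of the treatment assigned". The modified intent-to-treat set and the full analysis set keep the randomised arm, but neither is used for safety. Section 9.4.4 adds no attribution rule and no table by randomised arm.

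Departures from the plan are foreseen in three places:

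- Section 4.1: "exceptions are allowed during the surgery if the surgeon decides that changing the surgical plan is in the best interest of the patient". These are recorded as protocol deviations.
- Section 6.4: "justification for allowing clinical decision-making to overrule randomized treatment assignment will be documented".
- Section 9.3: the per-protocol set drops women whose rectopexy was not delivered as planned.

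The outcomes affected are named in section 8.2: "Perioperative measures of morbidity include operative time (a risk factor for operative morbidity), estimated blood loss, and intra-operative and post-operative complications". Rectal injury and ureteral injury are on that section's list of specific events. Section 4.1 makes the comparison of complications between the two rectopexies a secondary objective.

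**The concern.** Grouping by treatment received is harmless when what is received does not depend on the safety outcome. In surgery it can depend on it: an injury during one procedure may be the reason that procedure is not finished. If such a woman is then classed under the operation she ended up with, the event leaves the record of the operation in which it arose. If the rectopexy is abandoned, section 9.3 does not say whether she received it.

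What is at stake is the safety comparison of a novel operation, transvaginal sacrospinous rectopexy (TSR), with an established one, laparoscopic abdominal ventral rectopexy (LAVR). The arms are small, so one or two cases can alter the picture. Section 8.3.5 also calls for six-monthly adverse event summaries to the DSMB by treatment group without saying assigned or received, so the same gap reaches trial oversight.

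**Working it through.** The plan gives no safety sample size, complication rate or switch rate, so there is no stated figure to reproduce. The check has two parts.

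**Reading the sections together.**

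- A woman assigned to one rectopexy has a complication and is completed with the other. The plain reading of section 9.3 places her, and the event, under the second operation. Since she was exposed to both, her group is not in fact defined.
- A woman's rectopexy is abandoned and only a prolapse repair is done. Prolapse surgery is described under the study intervention in section 6.1.1, so she may well be in the safety set. Whether her column is TSR, LAVR or neither is not stated.
- No section says that the operation started governs, and no section says that the operation completed governs.

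**Size of one moved event.** Section 9.2 plans up to 120 women and section 6.3 allocates with equal probability, so n = 120/2 = 60 per arm. Assume x complications in each arm by randomisation, of which s in arm A lead to conversion to B.

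- By randomised arm: x/n against x/n, difference 0.
- By operation completed: (x − s)/(n − s) in A, (x + s)/(n + s) in B.
- Abandoned and not tabulated: (x − s)/(n − s) in A, x/n in B.

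With an assumed 10% rate (x = 6):

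- s = 1, converted: 5/59 = 8.5% against 7/61 = 11.5%, a false difference of 3.0 points.
- s = 2, converted: 4/58 = 6.9% against 8/62 = 12.9%, 6.0 points.
- s = 3, converted: 3/57 = 5.3% against 9/63 = 14.3%, 9.0 points.
- s = 1, abandoned and untabulated: 5/59 = 8.5% against 6/60 = 10.0%, 1.5 points.

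Over assumed rates of 5% (x = 3) and 15% (x = 9), one conversion gives:

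- 5%: 4/61 − 2/59 = 6.6% − 3.4% = 3.2 points.
- 15%: 10/61 − 8/59 = 16.4% − 13.6% = 2.8 points.

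The result of about 3 points per moved event is therefore not sensitive to the assumed rate. The error favours the arm in which the complication arose. With s = 0 it is zero. If every woman starts her assigned rectopexy, attribution to the procedure first started returns x/60 against x/60, so the false difference disappears.

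**An extreme case.** Suppose 3 injuries among 60 TSR starts and none among 60 LAVR starts, with 2 of the 3 women completed as LAVR. By procedure started, TSR minus LAVR is 3/60 − 0/60 = +5.0 points. By operation completed it is 1/58 − 2/62 = 1.7% − 3.2% = −1.5 points. All these counts are assumed.

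**The case against.** The case on the other side has real force:

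- Grouping safety by treatment received is common practice, and received is not the same word as completed. A woman in whom TSR was begun and caused an injury can reasonably be read as having received TSR.
- The exception in section 4.1 follows a sentence about rectopexy with or without prolapse repair as settled before surgery. It may concern only the prolapse component. Section 6.4 does reach the assigned arm, but does not mention conversion during surgery.
- A full switch is awkward to carry out. Section 6.2.1 gives TSR to urogynecologists, and for the other arm says "Laparoscopic abdominal ventral rectopexy will be performed by colorectal surgeons". Under section 10.1.1.1 each woman has her preoperative visit with the specialty of her own arm. The LAVR technique in section 6.1.1 warns against full-thickness rectal bites because of mesh contamination, so a rectal injury in TSR followed by mesh LAVR is not an obvious path.
- Deviations go to the IRB and the DSMB, events are assessed for relationship to the intervention with time of onset, and section 9.4.1 leaves the implementation of the analysis to an SAP written before database lock.

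Most of this stands. It means that misattribution is possible rather than certain, and probably infrequent. It does not supply a rule. Case-by-case review shows individual events but does not decide the column in which they are counted. Abandonment needs no second surgeon. A definition of received that is left open can also be settled after the events are known.

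**Conclusion.** The point holds as a gap in the grouping rule. Safety is analysed only by treatment received, the plan foresees departures from the assigned operation, and neither an attribution rule nor a table by randomised arm covers the woman whose complication changed her operation. At 60 per arm, each event that moves with a conversion distorts the risk difference by about 3 points, and each abandoned and untabulated case by about 1.5 points. These figures rest on assumed complication rates of 5% to 15% for conversion and 10% for abandonment. The number of such cases is unknown and may be zero, in which case nothing changes.

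Three stronger readings should be resisted. A reader might infer that such events will be charged to the other arm or lost; the documents do not support this, because section 9.3 leaves received undefined rather than equating it with completed. A reader might infer that the safety comparison is likely to change direction; that happens only in a constructed example with assumed counts. A reader might also infer that grouping by treatment received is itself wrong. It is not: for late, device-related events such as the mesh complications in section 2.3.1, actual exposure is the informative grouping.

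**What to change.** In section 9.3, and in the SAP before database lock:

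1. Attribute intra-operative and perioperative events, through the 2-week visit (the last point at which section 8.2 records perioperative morbidity), to the rectopexy first started. If neither was started, use the randomised arm. State which operative step marks the start of each rectopexy, since a prolapse repair may come first.
2. Keep in the safety population every woman in whom study surgery was begun.
3. Add adverse event and complication tables by randomised arm beside the as-received tables. In the as-received tables, show later events, including mesh-related ones, by actual exposure, and flag women exposed to both procedures. Carrying the first-started rule past the perioperative period would charge late mesh events in a converted woman to mesh-free TSR.
4. Report conversions and abandonments, with the triggering event, by randomised arm.

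Section 8.3.5 should also say which grouping the DSMB summaries use.

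The cost is a few lines of text and one extra set of tables. Form 06 (surgeon's report) and Form 19 (protocol deviation) already exist. Their content is not shown in the documents, so one added item recording the rectopexy started may be needed on Form 06.
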